13.5 Rationale for Alpha Test Tested

Not applicable.

Has been changed to read:

13.5 Sample Size

This is an open-label extension study. All subjects in a country where LCIG is not commercially available will be eligible to enroll if they meet the study's inclusion criteria and exclusion criteria.

Section 13.6 Power Needed
Delete: section title and text

13.6 Power Needed

Not applicable.

Section 13.7 Rationale for Power Needed
Delete: section title and text

13.7 Rationale for Power Needed

Not applicable.

Section 13.8 Power Calculation, Assumptions and Basis for Assumptions
Delete: section title and text

13.8 Power Calculation, Assumptions and Basis for Assumptions

Not applicable.

3.0 Abbreviations and Definitions of Terms

General Abbreviations

AE	adverse event
ATC	Anatomical Therapeutic Chemical (class)
BMI	body mass index
bpm	beats per minute
CGI-I	Clinical Global Impression – Improvement
CLES	Carbidopa/levodopa enteral suspension
CRF	case report form
CSR	Clinical Study Report
C-SSRS	Columbia Suicide Severity Rating Scale
DBP	diastolic blood pressure
DDT	data definition table
DSMB	data safety monitoring board
ECG	electrocardiogram
HLGT	High Level Group Term
HLT	High Level Term
kg	kilogram
LCIG	Levodopa-Carbidopa Intestinal Gel
LLT	Lowest Level Term
m	meter
max	maximum
MedDRA	Medical Dictionary for Regulatory Activities
mg	milligram
MIDI	Minnesota Impulsive Disorders Interview
min	minimum
mL	milliliter
mmHg	millimeters of mercury
N,n	number of observations
NA	not applicable
P(-Value)	exceedance probability for testing the null hypothesis
PCS	Potentially clinically significant
PD	Parkinson's Disease

PDQ-39	Parkinson's Disease Questionnaire
PEG-J	Percutaneous endoscopic gastrostomy – with jejunal extension tube
PT	Preferred Term
SAE	serious adverse event
SAP	statistical analysis plan
SBP	systolic blood pressure
SD	standard deviation
S.I.	System International
SOC	System Organ Class
TEAE	treatment-emergent adverse event
TESAE	treatment-emergent serious adverse event
TLF/T,L,F	tables, listings and figures
UKPDS	United Kingdom Parkinson Disease Society
UPDRS	Unified Parkinson's Disease Rating Scale
WHO-DD	World Health Organization – Drug Dictionary

Defined Terms

Day 1	First day of 3005 LCIG infusion
LDA	Duration of 3005 LCIG infusion
RFENDTN	Date of the last 3005 LCIG infusion
RFENDT2N	Date of the last 3005 PEG-J exposure
RFSTDTN	Date of the first 3005 LCIG infusion

Clinical Domain Abbreviations

AE	Adverse events
CM	Concomitant medication
DA	Drug accountability
DC	Device complications
DI	Device information
DM	Demographics
DS	Disposition
DV	Protocol deviations
EG	ECG test results
EX	Study drug exposure
HU	Healthcare utilization
IE	Inclusion/exclusion
KV	Key variables
LB	Laboratory test results
MH	Medical history
PE	Physical examination
QS	Questionnaire
SC	Subject characteristics
VS	Vital signs

4.0 Introduction

This statistical analysis plan (SAP), describes the analysis to be completed for Levodopa-Carbidopa Intestinal Gel (LCIG, also known as Carbidopa/Levodopa Enteral Suspension [CLES] in the United States) Study S187.3.005 (Study 3005), dated 17 December 2013, which incorporates Global Amendments 1, 2, 3 and 4 and UK Amendments 2 and 3.01. It contains a technical elaboration of the principal features of the statistical analyses described in the protocol and is intended to guide the statistical programming work for the interim analysis to be conducted following the interim database lock completed in October 2015 as well as for the final analysis to be summarized in the Clinical Study Report (CSR).

A previous interim analysis was completed as described in SAP Version 2. For the previous interim analysis, all subject assessments completed on or before 04 May 2012 were included.

For the October 2015 interim analysis, all subject assessments completed on or before 30 September 2015 (the "Cutoff Date") will be included in the analysis.

All analysis data sets and statistical output will be produced by the Biostatistics department of Quintiles, Inc, Research Triangles Park, North Carolina, USA using the SAS[®] system Version 9.4 or higher.¹

5.0 Summary of the Protocol and Amendments

5.1 Study Schedule of Assessments

[figure not shown]
The assessments performed in Study 3005 under Amendments 1, 2, 3 and 4 are summarized in the Study Schedules of Assessments (Appendix 12.1.1, Appendix 12.1.2, Appendix 12.1.3, and Appendix 12.1.4). Subject visit days should ideally match the target clinic visit days; however, a 14-day visit window will be allowed as necessary.

5.2 Overall Study Plan

This is a Phase 3B, open-label, multicenter study of the long-term safety and tolerability of LCIG in the treatment of approximately 275 advanced PD subjects with a good therapeutic response on LCIG with regard to the treatment of persistent severe motor fluctuations. The study will be conducted at approximately 70 centers.

Study 3005 is an extension study in the LCIG United States registration program. In this program, subjects who completed 12 weeks of treatment in double-blind double-dummy Study S187.3.001 (3001) or Study S187.3.002 (3002) were eligible to enroll in the 12-month open-label Study S187.3.003 (3003) and then in Study 3005. All subjects in Study 3001 and Study 3002 received a PEG-J and were randomized to receive either LCIG and placebo capsules or levodopa-carbidopa capsules and placebo gel. All subjects in Study 3003 received LCIG. Subjects who completed the 12-month open-label Study S187.3.004 (3004), were also qualified to enroll in Study 3005. Subjects in Canada were allowed to participate with a minimum of 6 months of exposure to LCIG in Study 3004.

Figure 1. LCIG United States Registration Program Overview

Following informed consent, subjects had their inclusion/exclusion criteria assessed prior to beginning treatment in Study 3005. Subjects are allowed to have a caregiver, if

appropriate, to assist them with study requirements, i.e., care of the pump and tubing, etc. and the caregiver will have been trained accordingly.

The initial LCIG dose in Study 3005 was identical to the dose that the subject was receiving at the end of the previous open-label LCIG study. Subsequent dose adjustments will be made as clinically indicated by the Investigator. In addition to the morning dose and the continuous infusion, subjects will be allowed to self-administer additional doses of LCIG to address immediate subjective needs, such as the deterioration of motor function. If a subject finds it necessary to self-administer an increasing number of extra doses ($> 5/\text{day}$) of LCIG, they will be instructed to contact the Investigator for appropriate follow-up care (adjustment of continuous infusion) as needed.

In this open-label study, a recommendation will be made to Investigators to withhold concomitant PD treatments if deemed medically safe and clinically appropriate. The initiation of additional PD medication may be medically indicated and is allowed at the discretion of the Investigator. Also, the dosages of these other PD medications can be adjusted upward or downward as needed based on the status of the subject's condition or the development of adverse effects; resumption of discontinued PD medications may also be necessary.

The final visit in the previous open-label LCIG study will provide baseline assessments for Study 3005. Subjects will be reassessed every 6 months for the appropriateness of the continuation of treatment with LCIG. If the subject is deemed inappropriate for continued treatment by the Investigator, the subject will be discontinued from treatment. Subjects who discontinue LCIG treatment will have the PEG-J removed, and a follow-up clinic visit will occur 1 week later.

Safety assessments include physical examination, neurological exam, orthostatic vital signs, weight, adverse event monitoring, assessment of impulsive behavior and sleep attacks, melanoma check, and special labs to monitor for vitamin deficiencies.

At each visit, adverse events or complications with the infusion device (i.e., the tubing system and the pump) will also be recorded and reported. Tube placement will be checked by radiography if there is a clinical indication that the tube has been displaced. The tube will be repositioned, if needed, to the original placement site just beyond the ligament of Treitz. At each visit the tube insertion site, including the stoma, will also be inspected. On a yearly basis, at a minimum, an assessment will be made of the need for a replacement of the PEG-J. The frequency of replacement should be in accordance with local practice.

Protocol Amendment 4 added the following efficacy assessments at US sites only: Parkinson's Disease Diary, the Unified Parkinson's Disease Rating Scale (UPDRS), and the Parkinson's Disease Questionnaire-39 (PDQ-39).

The protocol duration is planned until the finished product is available commercially in the respective countries where subjects are participating in the study.

5.3 Treatments

LCIG is a homogeneous suspension of levodopa (20 mg/mL) and carbidopa (5 mg/mL) in an aqueous intestinal gel (carboxymethylcellulose). LCIG is delivered to the proximal small intestine through a jejeunal extension tube inserted via percutaneous endoscopic gastrostomy (PEG-J). The intestinal gel is dispensed in a medication cassette reservoir of 100 mL, designed to be connected to a portable subject-operated pump. LCIG is to be administered over approximately 16 waking hours. At night, after disconnecting the pump for sleeping, the tubing is to be flushed with potable water.

Each subject's LCIG dose will be individually optimized. The initial LCIG dose will be identical to the dose that the subject was receiving at the end of the previous open-label LCIG study. Dose adjustments, either upward or downward, can be made at any time throughout the study based on the clinician's judgment of effectiveness. No dosing restrictions are given with relation to meals.

The total daily dose of LCIG infusion will be composed of three components: the morning dose, the continuous maintenance infusion dose, and extra doses. The morning dose is administered as a bolus infusion by the pump to fill the dead space of the intestinal tube and rapidly achieve therapeutic dose level (within 10 to 30 minutes). The total morning dose is typically 5 – 10 mL (100 – 200 mg levodopa) and will usually not exceed 15 mL (300 mg levodopa). The continuous maintenance dose is administered over approximately 16 waking hours. The infusion rate for the continuous maintenance dose is typically 2 – 6 mL/hour (40 – 120 mg levodopa/hour) and will usually be within 0.5 – 10 mL/hour (10 – 200 mg levodopa/hour). During the continuous infusion, subjects may self-administer a pre-set extra infusion dose (at intervals of no less than 2 hours) to address immediate medical needs, such as the rapid deterioration of motor function. The extra infusion dose will normally be set at 0.5 – 2.0 mL (10 – 40 mg levodopa). In rare cases a higher dose may be needed.

5.4 Data Safety Monitoring Board

Prior to the completion of the pivotal, Phase 3 studies, Study 3001 and Study 3002, a Data Safety Monitoring Board (DSMB) reviewed the safety data in accordance with the DSMB Charter. Planned safety analyses for the DSMB were presented in a separate document and are not discussed in any detail in the body of this SAP.

6.0 General Definitions, Methods, Naming Conventions and Data Handling

In order to avoid ambiguity during the analysis, a number of definitions and conventions for data handling are described in this section.

The following information for each subject will be summarized in a Key Variable (KV) derived dataset:

- Treatment group as described in Section 6.2.
- Reference dates as described in Section 6.4.1.
- Inclusion in subject samples as described in Section 8.1.1.

6.1 General Methodology and Presentation

The default summary statistics for quantitative variables will be the number of observations (n), mean, standard deviation (SD), median, minimum (min) and maximum (max), for those subjects with data.

All summary statistics will be rounded (using the SAS[®] function ROUND) and presented to one more decimal place than the raw value, except for the minimum and maximum values that will be presented with the same decimal precision as the raw value.

For qualitative variables, the number (n) and percentage (%) of subjects with non-missing data per category will be the default summary presentation, and where appropriate and present, the number of missing values as a "Missing" category.

Percentage values are to be rounded and presented to one decimal place, for example, 52.3%. If the calculated percentage is > 0.0% but < 0.1% then < 0.1% is to be presented in the relevant table and/or listing.

The exceedance probabilities for testing the null hypothesis will be denoted by "*P* value." *P* values are to be rounded (using the SAS[®] function ROUND) and printed with three decimals. *P* values below 0.0005 will be denoted as < 0.001.

6.2 Treatment Group Names and Labels

Statistical output (SAS[®] tables) will be presented. The treatment name/label to be used in the tables, listings and figures (TLFs) is defined in the table below.

Treatment Code Number	Treatment Description	Treatment Label
1	Levodopa-carbidopa intestinal gel (LCIG) supplied as a water suspension of 20 mg/mL levodopa and 5 mg/mL carbidopa	Levodopa-Carbidopa Intestinal Gel

6.3 Visit Names and Labels

The visit names/labels to be used in the analysis data sets and in the TLFs are defined in [Table 1](#) below.

Table 1. Visit Names and Labels

Visit Number	Visit Name	Visit Label
1	Baseline	Baseline
2	Month 6	Month 6
3	Month 12	Month 12
4	Month 18	Month 18
5	Month 24	Month 24
6	Month 30	Month 30
7	Month 36	Month 36
8	Month 42	Month 42
9	Month 48	Month 48
10	Month 54	Month 54
11	Month 60	Month 60
12	Month 66	Month 66
13	Month 72	Month 72
14	Month 78	Month 78
15	Month 84	Month 84
99	Follow-up	Follow-up

6.4 Day Numbers, Study Periods and Visit Windows: Related Definitions

6.4.1 General Definitions

Assessment days will be related to the date of the first infusion of 3005 study drug (First 3005 LCIG Infusion). Baseline is defined in Section [6.4.5](#) (Baseline Period). The Cutoff Date for the 2015 interim analysis will be 30 September 2015. Assessments and/or measurements performed after the Cutoff Date, adverse events or device complications with start dates after the Cutoff Date, and concomitant medications with start dates after

the Cutoff Date will not be included in the 2015 interim analysis. No cutoff date will be applied to the analysis for the final CSR.

The following reference dates will be defined for all subjects in the All Subjects Consented subject sample defined in Section 8.1.1.

- **Date of the First 3005 LCIG Infusion (Day 1, RFSTDTN):**

The actual dates of study drug administration are not recorded in the 3005 database. The dates when 3005 study drug is dispensed are recorded in the DA raw data panel. For analysis, the date of the first 3005 LCIG infusion will be defined as the first date that 3005 study drug was dispensed to the subject. The visit date recorded in the DM raw data panel will be used if the date the first study drug was dispensed is not available.

The date of the first 3005 LCIG infusion will be defined as Day 1 and is the key variable RFSTDTN and is used in the calculation of relative days.

- **Date of the Last 3005 LCIG Infusion (RFENDTN):**

For subjects who have prematurely discontinued or completed the study, the date of the last 3005 LCIG infusion will be the earliest of 1) the date of last study drug administration collected on the DS raw data panel, 2) the date of discontinuation or study completion collected on the DS raw data panel and 3) the Cutoff Date (interim analysis only).

For the 2015 interim analysis, the date of the last 3005 LCIG infusion for all ongoing subjects will be the Cutoff Date.

- **Duration of 3005 LCIG Infusion (LDA):**

The Duration of 3005 LCIG Infusion or exposure to treatment is equal to the day number of the Last 3005 LCIG Infusion (LDA) and is derived as follows from the previous two dates:

$$\text{LDA (days)} = (\text{Date of the Last 3005 LCIG Infusion [RFENDTN]} - \text{Date of the First 3005 LCIG Infusion [RFSTDTN]}) + 1$$

LDA then indicates the relative day of the last 3005 LCIG infusion for each subject.

- **Date of Last 3005 PEG-J Exposure (RFENDT2N):**

LCIG is administered as part of a therapeutic system that includes devices and implantation procedures. Subjects who discontinue LCIG therapy are to have their PEG-J removed.

For subjects who have prematurely discontinued or completed the study, and have reported a final PEG-J removal on the DI raw data panel that is after their last day of study drug administration and before the Cutoff Date (interim analysis only), their date of last 3005 PEG-J exposure will be the date of PEG-J removal. For all other subjects who have prematurely discontinued or completed the study, their date of last 3005 PEG-J exposure will be the earlier of 1) the date of discontinuation or study completion collected on the DS raw data panel, and 2) the Cutoff Date (interim analysis only).

For the 2015 interim analysis, the date of the last 3005 PEG-J exposure for all ongoing subjects will be the Cutoff Date.

The date of the last 3005 PEG-J exposure is the key variable RFENDT2N.

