11.6 Flow Chart of Study Assessments

All study assessments will be conducted as indicated in [Table 2](#), which displays the frequency and timing of all measurements. Subject visit days should ideally match the target clinic visit days; however, a ± 14 day visit window will be allowed as necessary for the 6 Monthly visits and a ± 7 day visit window will be allowed for clinical supply visits. Every attempt should be made to bring the subject back on the target visit day.

Table 2. Flow Chart of Study Assessments

Visit	Baseline	6 Monthly Visit	Termination/ Transfer to Commercial	Follow-up*
Day	Final Assessment in Previous Study	+/- 14 Days	--	Termination Visit + 7 Days
Informed consent	X			
Inclusion/exclusion	X			
Physical exam	X ^a	X	X	
Neurological Exam	X ^a	X	X	
Weight	X ^a	X	X	
Vital signs	X ^a	X	X	X
12-lead ECG	X ^a	X ^b	X	
Clinical labs	X ^a	X ^b	X	
Folic Acid, Vitamins B6, B12, Methylmalonic Acid (MMA), and Homocysteine Levels	X ^a	X	X	
β-HCG ^c	X ^a	X	X	
Adverse events**	X ^a -----X			
Concomitant medication	X ^a	X	X	X
Sleep attacks	X ^a	X	X	
Melanoma check	X ^a	X ^d	X	
Determination of continued benefit***	X	X		
MIDI	X ^a	X	X	
C-SSRS ^f	X ^a	X	X	X
Complications with infusion device	X ^a	X	X	
Inspection of stoma	X ^a	X	X	X
Assessment of the need to replace PEG-J****	X	X ^d		
Dispensing of study drug	X-----Every 6 weeks ^e -----			
Daily Dosing Diary ^g		X	X	

Table 2. Flow Chart of Study Assessments (Continued)

Visit	Baseline	6 Monthly Visit	Termination/ Transfer to Commercial	Follow-up*
Parkinson's Disease Diary ^g		X	X	
UPDRS ^h		X	X	
PDQ-39 ^h		X	X	
Removal of PEG*****			X	

- * This visit needs to be performed only if PEG-J is removed, or if the subject does not continue to receive drug after termination.
- ** Collection of adverse events is an ongoing and continuous process, not only occurring during site visits.
- *** The decision to continue subjects on LCIG treatment will be dependent upon Principal Investigator's clinical judgment.
- **** On a yearly basis, the LCIG system check needs to be evaluated by the study gastroenterologist; frequency of replacement should be in accordance with local practice.
- ***** For subjects deemed inappropriate for continued treatment by the Investigator, or for subjects who elect not to continue LCIG treatment, the PEG-J will be removed, and a follow-up clinic visit will occur 1 week later.

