13.3 Statistical Methods

Safety Analysis

The Safety Population will be used for the analysis of the safety and tolerability data.

Adverse events will be coded using the Medical Dictionary for Regulatory Activities (MedDRA). A treatment-emergent adverse event (TEAE) is defined as any adverse event that begins or worsens in severity on or after the first dose of study drug in the current study and within 30 days of the end of LCIG treatment in the current study. For subjects transferring to commercial product, the end of treatment in the current study will be the last dose of study drug. For subjects who are discontinuing LCIG treatment, the end of treatment in the current study will be the removal of the PEG-J tube. The following summaries of TEAE's will be prepared:

- Incidence of treatment-emergent adverse events
- Incidence of treatment-emergent serious adverse events

- Incidence of treatment-emergent adverse events resulting in study termination
- Incidence of treatment-emergent adverse events of special interest

The following additional analyses of safety will also be prepared:

- Summary of vital sign and weight values and mean change from Baseline over time
- Incidence of potentially clinically significant vital sign and weight values
- Summary of clinical lab values and mean change from Baseline to Endpoint
- Summary of special lab values and mean change from Baseline over time
- Incidence of potentially clinically significant clinical lab values
- Summary of MIDI at Baseline and during treatment
- Summary of C-SSRS
- Incidence of device complications

Efficacy Analysis

The Efficacy Population will be used for analyses of efficacy. The mean change from baseline to endpoint will be summarized for the following efficacy endpoints.

- "Off" time as measured by the Parkinson's Disease Diary
- "On" time without troublesome dyskinesia (sum of "On" time without dyskinesia and "On" time with non-troublesome dyskinesia) as measured by the Parkinson's Disease Diary
- UPDRS total score, Parts I, II, III and IV scores, and dyskinesia item score
- PDQ-39 summary index and domain scores

For the analysis of change from baseline in efficacy measures, each subject's baseline will be their baseline measure in the first LCIG study in which they participated (e.g., Study S187.3.001, S187.3.002 or S187.3.004).

Additional Analysis

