6.4.6 Treatment Period

Data collected on the Date of the First 3005 LCIG Infusion (Day 1) will be assigned to the Baseline Period. However, adverse events and concomitant medications starting on Day 1 will be assigned to the Treatment Period (worst case scenario).

A Gap Period (number of days) is defined to include data collected after the end of the relevant Treatment Period in the analysis. For this study, the Gap Period will be 30 days for adverse events and 1 day for all other assessments.

For efficacy assessments the Treatment Period is defined as the Period from the Date of the First 3005 LCIG Infusion up to and including the Date of the Last 3005 LCIG Infusion + Gap Period (1 day). For safety assessments the Treatment Period is defined as the Period from the Date of the First 3005 LCIG Infusion up to and including the Date of the Last 3005 PEG-J Exposure + Gap Period (30 days for adverse events and 1 day for all other assessments).

The Endpoint value for a variable is defined as the last non-missing value assigned to the Treatment Period for the subject.

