6.4.8 Visit Windowing Conventions

Assessments will be assigned to the Baseline Period if the date is on or before the Date of the First 3005 LCIG Infusion as defined in Section 6.4.1 and to the Post-Treatment Period if the date is after the end of the relevant Treatment Period as defined in Section 6.4.6.

Assignment of assessments to visits during the Treatment Period will use visit windows based on the day of the assessment relative to the Date of the First 3005 LCIG Infusion as described in Table 2 below.

Table 2. Visit Windowing Conventions

Visit Label	Target Visit Day	Study Day Range
Baseline	≤ 1	
Month 6	180	2 to 270
Month 12	360	271 to 450
Month 18	540	451 to 630
Month 24	720	631 to 810
Month 30	900	811 to 990
Month 36	1080	991 to 1170
Month 42	1260	1171 to 1350
Month 48	1440	1351 to 1530
Month 54	1620	1531 to 1710
Month 60	1800	1711 to 1890
Month 66	1980	1891 to 2070
Month 72	2160	2071 to 2250
Month 78	2340	2251 to 2430
Month 84	2520	> 2430

If a subject has two or more assessments in the same visit window, the assessment closest to the target visit day will be used. If two assessments are equidistant from the target visit day, the later assessment will be used.

Each reported post-baseline lab and vital sign measurement shall be evaluated to determine if it meets potentially clinically significant criteria. For all other analyses of

labs and vital signs, if two measurements are on the same date, the average will be calculated and treated as the value for that date.

6.4.9 3005 Treatment Year

The following events will be summarized by 3005 Treatment Year using the study day intervals described in [Table 3](#) below: premature study discontinuations, prevalence of concomitant anti-parkinsonian medication use, the incidence and prevalence of adverse events, the incidence of device complications, and the number of PEG tube and J-tube replacements.

Table 3. 3005 Treatment Year

3005 Treatment Year	Study Day Range
Year 1	2 to 365
Year 2	366 to 730
Year 3	731 to 1095
Year 4	1096 to 1460
Year 5	1461 to 1825
> Year 5	> 1825

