For a missing/incomplete stop date the maximum of the following will be imputed:

- The minimum of the latest possible stop date and the date of last administration of investigational study drug
- The earliest possible stop date
- The earliest possible start date

Here, the earliest (latest) possible date is defined as:

- The date itself if it is possible
- The date of the first (last) day of the month, if month and year are available but the day is missing
- The date of the first (last) day of the year, if year is available but day and month are missing
- A very early (late) date, for example, 01JAN1000 (01JAN3000), if the date is completely missing

From this data the following will be determined and used for presentation in the applicable tables and listings:

- Treatment-Emergent Adverse Events (TEAEs): Defined as AEs which started on or after the Date of the First 3005 LCIG Infusion and within 30 days of the Date of the Last 3005 PEG-J Exposure.
- Treatment-Emergent Serious Adverse Events (TESAEs): Defined as TEAEs regarded by the Investigator as Serious.
- TEAEs that are at least possibly related to the therapeutic system: Defined as TEAEs assessed as having a "Possible" or "Probable" relationship to the investigational therapeutic system and includes those events where the relationship is missing.
- Severe TEAEs: Defined as TEAEs assessed as being "Severe" in intensity and includes those events where the severity is missing.
- TEAEs that led to premature discontinuation: Selected as those events where: "Led to Study Termination" is indicated as "Yes."
- TEAEs with fatal outcome as reported on the "Adverse events" CRF.
- TEAEs in the following categories have been defined as TEAEs of special interest:
 - Procedure and device associated events
 - Polyneuropathy (broad search as well as narrow search)
 - Weight loss

- Cardiovascular fatalities
- Respiratory tract aspiration including aspiration pneumonia/pneumonitis

TEAEs are included in a category of special interest based on their PT and, in the case of cardiovascular fatalities, their outcome. The list of PT's assigned to each category is included as Appendix 12.4. Only TEAEs where an outcome of "Fatal" has been reported on the "Adverse Event" CRF are to be included in the category of cardiovascular fatalities. All events with PT's other than those assigned to the procedure and device associated AESI category will be included in summaries of events that are not procedure and device related.

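### SAP 6.4.1 ignores a PEG-J removal recorded on the last infusion day, so the safety windows may depart from the protocol if the DS discontinuation date differs from the removal date

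*SAP*

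**What the plan says.** SAP 6.4.1 gives two routes to RFENDT2N for subjects who have discontinued or completed. The removal date is used for those who "have reported a final PEG-J removal on the DI raw data panel that is after their last day of study drug administration"; at the interim, a removal must also precede the cutoff. For the rest, last PEG-J "exposure will be the earlier of 1) the date of discontinuation or study completion collected on the DS raw data panel" and, at the interim only, the Cutoff Date.

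Protocol 13.3 puts no such condition on the removal date: "For subjects who are discontinuing LCIG treatment, the end of treatment in the current study will be the removal of the PEG-J tube".

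RFENDT2N then drives several safety definitions:

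- SAP 6.4.6 closes the safety Treatment Period at last PEG-J exposure plus a "Gap Period (30 days for adverse events and 1 day for all other assessments").
- SAP 8.5.1 counts an event as treatment-emergent if it starts "within 30 days of the Date of the Last 3005 PEG-J Exposure".
- SAP 8.3.2 computes PEG-J exposure from it.
- SAP 8.5.1, 8.5.5.1 and 8.5.5.2 use it, plus 30 days, to decide who is in each Treatment Year denominator for adverse events, device complications and tube replacements.

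SAP 10.1, which lists departures from the protocol analysis, does not mention the condition on the removal date.

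**The concern.** Same-day removal is a realistic case. Protocol Table 2 puts tube removal in the Termination column. At US sites the UPDRS is in that column too, and Protocol 11.2.2 times it 1 to 4 hours after the first morning dose. A US subject who does everything at one visit infuses in the morning and loses the tube that day.

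For that subject the SAP sets aside a known removal date and substitutes an administrative one. A subject whose tube is removed one day later keeps the removal date. If the two dates differ, the first subject's safety window no longer starts from the event that the protocol names, and assessments made after treatment ended could be counted as Treatment Period data.

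**Working it through.** The plan gives no figure for this rule, so there is none to reproduce. The check applies the rule to an assumed subject.

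**Is *after* strict?** The SAP spells out inclusive limits when it wants them, for example in 6.4.8: "Assessments will be assigned to the Baseline Period if the date is on or before the Date of the First 3005 LCIG Infusion". Tube removal is recorded as a date (SAP 8.5.5.2), so a time order within one day cannot satisfy the condition. The natural coding is removal date > last drug date.

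**Inputs**

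- Last infusion and removal both on Day 700 (assumed); final analysis, so no cutoff.
- g = DS discontinuation date minus removal date. The documents do not give g, so it is varied.
- Gap Periods of 30 days (AEs) and 1 day (other safety data), from SAP 6.4.6.
- Year 2 is Days 366 to 730 and Year 3 is Days 731 to 1095, from SAP Table 3.

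**Formulas**

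- As written, the strict condition fails, so RFENDT2N = 700 + g.
- With *on or after*, RFENDT2N = 700 for every g.
- AE window end = Treatment Period End Day = RFENDT2N + 30. Other safety window end = RFENDT2N + 1. PEG-J exposure in days equals the day number of RFENDT2N.

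| g (days) | RFENDT2N as written | AE window to | Other safety data to | Shift against *on or after* (700 / 730 / 701) | In Year 3 denominators: written / inclusive |
|---|---|---|---|---|---|
| −3 | 697 | 727 | 698 | −3 | no / no |
| 0 | 700 | 730 | 701 | 0 | no / no |
| +1 | 701 | 731 | 702 | +1 | yes / no |
| +7 | 707 | 737 | 708 | +7 | yes / no |
| +14 | 714 | 744 | 715 | +14 | yes / no |
| +30 | 730 | 760 | 731 | +30 | yes / no |

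The shift is g throughout. The −3 row assumes that removal is compared with the recorded last-administration date. If it is compared with the derived RFENDTN, which is itself capped at the DS date, removal falls after it and the removal date is used.

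With removal on Day 701, one day after the last infusion, the written and inclusive rules agree for every g tried.

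**What +7 would mean.** Table 2 schedules Follow-up at "Termination Visit + 7 Days", with vital signs and C-SSRS. If the DS date were that visit, Day 707 lies inside the window to Day 708, and both count as Treatment Period data; under the inclusive rule the window closes on Day 701. By-visit vital signs could also change. Day 707 falls in the Month 24 window (Days 631 to 810, target 720), and 720 − 707 = 13 is closer than 720 − 700 = 20. The Follow-up reading would therefore displace the Day 700 reading, unless another reading is closer still. PEG-J exposure would be overstated by 7/700 = 1.0% for this subject.

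**The case against.** The strongest reply is that the most natural scenario gives no error. If the last infusion, removal and Termination visit share a date, the plainest reading of a DS discontinuation date is that same date, so g = 0. Table 2 treats Follow-up as separate from termination, and nothing equates the DS date with Follow-up or with the date of last contact used in listing DSL002. This stands: the +7 case is an assumption. It does not settle the matter, because neither document ties the DS date to tube removal. SAP 6.4.1 also takes the earliest of the last-administration and discontinuation dates when it defines the last infusion, so it allows for DS dates that differ.

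Four further limits stand:

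- Same-day removals may be few. Protocol 10.1.4 requires endoscopic retrieval, which a site may book for another day.
- Protocol 12.1.1 asks for AE reporting for 30 days after termination including removal, so a longer window would add few events. The narrow exception is SAEs spontaneously reported within 30 days of the last visit (Protocol, text just before 12.2.2).
- Individual tube durations (SAP 8.5.5.2) use the recorded removal date and turn to RFENDT2N only when it is missing.
- LCIG exposure and efficacy use the last infusion date. Subjects transferring to commercial product keep the tube (Protocol 11.0).

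A reader might also infer that Follow-up vital signs or C-SSRS would become Endpoint values. The planned outputs do not support that. SAP 9.11.3 summarises vital signs by visit and by incidence of potentially clinically significant values, and SAP 8.5.5.5 reports C-SSRS incidence at any time in the Treatment Period. Protocol 13.3 plans safety change to Endpoint for clinical laboratory values only, and Table 2 schedules none at Follow-up.

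**Conclusion.** The gap in the rule is real. A removal on the last infusion day is excluded from the removal-date route, which departs from Protocol 13.3 and is undeclared in SAP 10.1. Its effect is conditional and equals the DS date minus the removal date: none if they coincide, and 7 days under the assumption that the DS date is the Follow-up visit. A Treatment Year denominator changes only for a subject whose Treatment Period End Day crosses a year boundary within that gap.

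It would be tempting to conclude that these subjects always receive a later date and a wrong safety window. The documents do not support that, because they never say that the DS date is later than removal. The number of subjects is not given and may be zero. Safety reporting is descriptive and no alpha is set (Protocol 13.4), so no test is at risk. Severity: minor.

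**What to change.** In SAP 6.4.1, change the condition so that the final PEG-J removal date is used when it falls *on or after* the last day of study drug administration. This restores the protocol's definition for same-day removals. It leaves later removals unchanged and still sends a removal dated before the last drug day to the fallback. The cost is two words and one comparison operator, using data already collected.

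A sentence saying what the DS discontinuation date represents would help wherever the fallback applies. The interim cutoff wording can stay, since the fallback already caps the date at the Cutoff Date. To see whether any output moves, count the discontinued subjects whose removal date equals their last drug date and whose DS date differs. If the strict rule is intended, SAP 10.1 should list it as a change from the protocol and give the reason.
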